### Analysis Populations:

The main population for non-safety analysis will be the As Exposed Exercise Compliant Set.

Safety will be analyzed using the Safety Set.

1. As Exposed Exercise Compliant Set

The As Exposed Exercise Compliant Set (AEECS) consists of all randomized subjects who have at least one valid non-safety assessment after randomization, specifically we have

- post-randomization product (cigarette or *IQOS*) use experience if randomized to *IQOS*, *IQOS*-2 or cigarette arm or
- no product use if randomized to the SA arm,

and who attended at least 34 of 38 (~90%) of the exercise training sessions except the subjects in IQOS-2 arm. The AEECS will be analyzed by actual exposure (product use exposure).

## 2. Full Analysis Set

The Full Analysis Set (FAS) consists of all randomized subjects who have at least one postrandomization product (cigarette or *IQOS*) use experience if randomized to *IQOS*, *IQOS*-2 or cigarette arm, and who have at least one valid non-safety assessment after randomization. All subjects in the SA arm who fulfil these requirements, except the product use experience, are part of this set as well. The FAS will be analyzed by randomized study arm.

3. Safety Set

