#### **Study Design:**

This is a randomized, controlled, open-label, 4-arm parallel group study with stratification by daily cigarette consumption over the past 12 months prior to V1 as reported during V1 (i.e. 10 to 19 cigarettes or >19 cigarettes per day) and sex (Figure 1).

A sufficient number of healthy adult smokers will be screened and enrolled after checking that all eligibility criteria have been met, in order to reach 90 randomized subjects.

Smokers will be randomized as follows with a 5:5:5:3 ratio according to strata:

- 1. switch to *IQOS* use + participation in training program: *IQOS*-1 arm, 25 subjects
- 2. continue cigarette smoking + participation in training program: **Cigarette arm**, 25 subjects
- 3. smoking abstinence + participation in training program: SA arm, 25 subjects
- 4. switch to *IQOS* use only: *IQOS-2* arm, 15 subjects

When 90 randomized subjects are reached, further enrollment will be stopped. Subjects already enrolled in the study will still be eligible for randomization. From randomization, subjects will be instructed to use their allocated product or stay smoking abstinent until the end of the study. Drop-outs will not be replaced.

Acute effect on VO2max and exercise capacity of switching to *IQOS* will be assessed one week after randomization before initiating the training program, and the combined effect of switching and exercise training will be assessed one week after completion of the 12-week training program.

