# 7.2 Information on the Risk of Smoking and Smoking Cessation Advice and Debriefing on *IQOS*

All subjects included in the study will be advised that the best way of preventing the development of smoking-related diseases is to stop smoking. Only subjects who are not planning to quit smoking cigarettes will be eligible for the study.

From V1 onwards, information on the risks of smoking and smoking cessation advice will be given to all subjects (Appendix 1). This will take the form of a brief interview according to WHO recommendations (54). In addition, a debriefing of subjects will be done to address any intended or unintended beliefs participants have about *IQOS*. The goal of the debriefing is to

Data and information contained in this document are considered to constitute trade secrets and confidential commercial information, and the legal protections provided to such trade secrets and confidential information are hereby claimed under the provisions of applicable law. No part of this document may be publicly disclosed without the written consent of Philip Morris Products S.A

Philip Morris Products SA	Clinical Study Protocol	Confidential
P1-EXC-01-EU	Version 3.0 / 2 May 2019	Page 60 of 151

ensure that subjects have an accurate understanding of *IQOS* risks including an understanding that *IQOS* has not yet been demonstrated to be less harmful than cigarettes.

Any enrolled subject, who is willing to attempt quitting during the study will be encouraged to do so and will be referred to appropriate medical services.

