### 12.4.2 Full Analysis Set

The Full Analysis Set (FAS) consists of all randomized subjects who have at least one postrandomization product (cigarette or *IQOS*) use experience if randomized to *IQOS*, *IQOS*-2 or cigarette arm, and who have at least one valid non-safety assessment after randomization. All subjects in the SA arm who fulfil these requirements, except the product use experience, are part of this set as well. The FAS will be analyzed by randomized study arm.

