6 SAMPLE SIZE JUSTIFICATION

The sample size of 20 per arm (smoking abstinence with training, IQOS with training, continued cigarette smoking with training) was determined based on previously published results, which reported a standard deviation of 14 mL/kg/min in VO₂max in the change

Confidentiality Statement

Philip Morris Products SA.	Statistical Analysis Plan	Confidential
P1-EXC-01-EU	Final 2.0	Page 30 of 71
Related to PMI-RRP-WKI-112487		SAD DI EYC OI EU

between groups which continued smoking and those who were smoking abstinent after participating in a 12-week training program (Albrecht, et al. 1998). This sample size allows a probability of 90% that the half-width of the 95% confidence intervals between two arms have a precision of approximately 10.3 mL/kg/min.

For example, if the mean difference in change between the cigarette arm and smoking abstinence arm was 12 mL/kg/min after training, we expect that if the experiment were repeated many times then on average 90% of the time the 95% confidence intervals of the mean differences between two arms will be within 1.7 and 22.3. To allow for a dropout rate of approximately 20%, the sample size will be 25 per arm. The IQOS-2 arm without training will mainly serve as a secondary analysis to the IQOS-1 arm with training, and the drop-out rate in this arm is expected to be lower. Therefore, only 15 subjects will be randomized to this arm.

CHANGES FROM THE PROTOCOL SPECIFIED STATISTICAL 7 ANALYSES

An exploratory analysis of VO2max and exercise capacity will be carried out on subjects with additional biochemical verification of smoking status.

8 **ANALYSIS SETS**

The main population for non-safety analysis will be the As Exposed Exercise Compliant Set. Safety will be analyzed using the Safety Set.

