8.1 Full Analysis Set

The Full Analysis Set (FAS) consists of all randomized subjects who have at least one postrandomization product (cigarette or IQOS) use experience if randomized to IQOS, IQOS-2 or cigarette arm, and who have at least one valid non-safety assessment after randomization. All subjects in the SA arm who fulfil these requirements, except the product use experience, are part of this set as well. The FAS will be analyzed by randomized study arm.

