9.1.1 Stratified Presentation

Stratification criteria for the evaluation are:

- Randomized study arm Cigarette, IQOS-1, smoking abstinence (SA), IQOS-2) randomized arm.
- Product use (actual arm) i.e. actual product use exposure categorized based on self-reporting and biochemical verification according to Section 5.5.1 "Product Use Pattern":

Confidentiality Statement

Data and information contained in this document are considered to constitute trade secrets and confidential commercial information, and the legal protections provided to such trade secrets and confidential information are hereby claimed under the provisions of applicable law. No part of this document may be publicly disclosed without the written consent of Philip Morris Products S.A

Philip Morris Products SA.	Statistical Analysis Plan	Confidential
P1-EXC-01-EU	Final 2.0	Page 34 of 71
Related to PMI-RRP-WKI-112487		SAP_P1-EXC-01-EU

- o Cigarette,
- o IQOS-1,
- Smoking Abstinence (SA),
- IQOS-2,
- Dual users considered for IQOS-1 (Dual-1),
- Dual users considered for IQOS-2 (Dual-2),
- Cigarette consumption at V1 (10 to 19 cigarettes, more than 19 cigarettes per day)
- Sex (male, female)
- Age (<50, ≥ 50 years i.e. $21 \le Age < 50$ and $50 \le Age \le 65$])

The main stratification criterion for the evaluation is the actual product exposure, whereas data will be listed by randomization arm.

Further stratification by cigarette consumption and sex will be done for the analysis of VO_2max and exercise capacity and where explicitly defined. Further stratification by age and BMI will be done only where explicitly defined (e.g. for demographic data).

The AEECS, AEBECS and the Safety Set will be analyzed by actual study arm (product use exposure). The FAS will be analyzed by randomized study arm.

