9.6.1.3 Supportive/Sensitivity Analyses

If deemed appropriate, selected endpoint analyses will additionally be performed for the FAS.

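### The FAS, the only set analysed by randomised arm, requires product use after randomisation in the IQOS-1, IQOS-2 and cigarette arms but waives it for SA, so exclusion depends on behaviour in an arm-specific way

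*Protocol*

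**What the plan says.** The rule is the same in the protocol synopsis, protocol 12.4.2 and SAP 8.1. It opens: "The Full Analysis Set (FAS) consists of all randomized subjects who have at least one postrandomization product (cigarette or *IQOS*) use experience". This applies to subjects allocated to IQOS-1, IQOS-2 or cigarette, who must also have a valid non-safety assessment after randomisation. The SA arm is then treated separately: "All subjects in the SA arm who fulfil these requirements, except the product use experience, are part of this set as well".

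On grouping, SAP 8.1 states: "The FAS will be analyzed by randomized study arm". SAP 9.1.1 repeats this and assigns the AEECS, the AEBECS and the Safety Set to actual product use.

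On role, SAP section 8 says: "The main population for non-safety analysis will be the As Exposed Exercise Compliant Set". The FAS is supportive, under SAP 9.6.1.3: "If deemed appropriate, selected endpoint analyses will additionally be performed for the FAS". The table list in SAP 13.2 nevertheless includes a full block of FAS models and summaries for VO2max (Tables 15.2.2.1.6 to 15.2.2.1.10) and exercise capacity (Tables 15.2.2.2.6 to 15.2.2.2.10).

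**The concern.** An analysis by randomised arm protects against selection only if entry does not depend on what subjects do after allocation. Here it does, and the condition bites in three arms and not in the fourth.

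The behaviour that triggers exclusion, using neither cigarettes nor IQOS, is close to the factor under study. Protocol 4.2 assumes that removing CO exposure improves exercise capacity and the response to training. A cigarette-arm subject who stops at V3 is therefore one whom the protocol would expect to do better than continuing smokers, and the FAS would leave that subject out.

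Nothing else in the plan removes such a subject. Stopping tobacco is not a reason for discontinuation in protocol 5.2, and the V4 and V43 tests are still due. Product use before each test is voluntary (protocol 6.3.2), so it does not guarantee a qualifying use. Quitting is also allowed for. Protocol 7.2 says: "Any enrolled subject, who is willing to attempt quitting during the study will be encouraged to do so".

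The FAS matters because every other set is grouped by actual use. The main set carries its own product-use condition for the product arms (protocol 12.4.1, SAP 8.3), so the same subject is missing there too.

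**Working it through.** **Definition check.** Take a subject with at least one valid non-safety assessment after randomisation and no cigarette or IQOS use from V3 onward.

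| Randomised arm | Planned n | In the FAS? |
|---|---|---|
| IQOS-1 | 25 | No |
| IQOS-2 | 15 | No |
| Cigarette | 25 | No |
| SA | 25 | Yes |

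The planned numbers come from the 5:5:5:3 ratio: 90 × 5/18 = 25 and 90 × 3/18 = 15. The condition therefore applies to 25 + 15 + 25 = 65 planned subjects and is waived for 25. The qualifying product is either a cigarette or IQOS, so an IQOS-arm subject who only smokes stays in. Only those who use neither are dropped.

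**The plan's precision figure, as a yardstick.** Inputs from protocol 12.2: SD 14 mL/kg/min, 20 per arm, 95% interval, 90% probability. The half-width is

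t(0.975, 38) × 14 × √(2/20) × √(χ²(0.90, 38)/38).

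The first three factors give 8.96 and the last is about 1.14, so the result is 10.23. It is 10.25 if conditioned on the interval covering the true difference. The plan states about 10.3, so its figure is reproduced. Inflating 20 for 20% dropout gives 20/0.8 = 25 per arm.

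**Shift per excluded quitter.** Suppose a cigarette arm of 25 has 24 continuing smokers with mean change m and one quitter with change m + d.

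- Mean of all 25: (24m + m + d)/25 = m + d/25.
- Mean under the FAS rule: m.
- Difference: d/25. SA is unchanged, so SA versus cigarette moves by the same amount.

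The documents give no value for d.

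- d = 12, the illustrative SA versus cigarette difference in protocol 12.2: 12/25 = 0.48 mL/kg/min.
- d = 2 to 5 (assumed): 0.08 to 0.20 mL/kg/min.

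Two quitters double these figures. Against the half-width, 0.48/10.3 is about 5%.

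**Expected numbers.** No immediate-quit rate is given either. For an assumed rate q, the cigarette arm would lose 25q subjects on average, and at d = 12 the mean would shift by 12q.

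| Assumed q | Dropped of 25 (cigarette) | Shift at d = 12 (mL/kg/min) |
|---|---|---|
| 2% | 0.5 | 0.24 |
| 5% | 1.25 | 0.60 |
| 10% | 2.5 | 1.20 |

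These are differences in simple means with complete data. The covariate-adjusted model would not reproduce them exactly.

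**The case against.** The best defence is that the rule will rarely bite. A single cigarette or HeatStick at any time after randomisation keeps a subject in, so later quitting, relapse and dual use exclude nobody. Inclusion criterion 5 requires that subjects have no plan to quit within 6 months. Cigarette and IQOS subjects are asked, if willing, to use their product before the V4 and V43 tests, and those in training before each session as well. IQOS subjects also have a guided trial when they receive the device (protocol 6.3.1). The documents do not say whether that trial counts as use. If it does, almost no IQOS-arm subject could be dropped and the effect would fall mainly on the cigarette arm. All of this stands and limits the weight of the point.

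A reader might infer from the repeated cessation advice that many subjects would be removed. The schedule does not support that. Advice is given at V1 and V2, before randomisation, and then at V14 and V28, about 40 and 68 days after V3. Advice that late cannot produce a subject with no use at all unless that subject had already stopped at V3.

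It is also fair to say that the FAS is supportive, that no hypothesis is tested, and that exclusions will be visible. Table 15.2.1.3 reports the reasons for exclusion and Table 15.2.1.4 the numbers by arm. Visibility helps the reader but does not put the excluded subjects back into the FAS models. Neither document gives a reason for treating SA differently.

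**Conclusion.** The asymmetry is explicit and identical in all three places, and it affects the only set grouped as randomised. It is a minor point, worth correcting because correction is nearly free. If no product-arm subject goes without both products from V3 onward, the current and the amended definitions give the same results.

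For SA versus cigarette, the likely direction is overstatement. The size rests on an assumed d and an assumed number of quitters. The direction rests on the protocol's premise about CO. The value d = 12 is a difference between arm means used as an example, not an estimate of a quitter's extra gain.

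Two stronger readings are not supported. The first is that the bias runs the same way in every arm. Protocol 2.1.1 attributes the effect of smoking mainly to CO and regards nicotine's effect as minor, and protocol 4.2 expects reduced CO to help IQOS-1 as well as SA. On that view an IQOS-arm quitter need not gain more than an IQOS user, so no direction is claimed for the IQOS arms. IQOS versus cigarette carries the same condition on both sides. The second is that removing the condition would fully restore the randomised comparison. The VO2max model in SAP 9.6.1.1.1 may retain COHb at each visit and self-reported cigarette consumption since randomisation, and it evaluates estimates at each arm's own covariate means. SAP 13.2 lists variable selection for the FAS too (Tables 15.2.2.1.9 and 15.2.2.2.9). That is a separate matter.

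**What to change.** In the protocol synopsis, protocol 12.4.2 and SAP 8.1, delete the product-use condition together with the sentence that exempts SA. Define the FAS in all four arms as every randomised subject with at least one valid non-safety assessment after randomisation, analysed by randomised arm.

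The cost is one sentence in three places. It needs no new data, visits or tables, because Tables 15.2.1.3 and 15.2.1.4 already cover exclusions. The change removes the arm-dependent exclusion only and leaves the choice of covariates in the FAS models as it is.

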## **Confidentiality Statement**

Philip Morris Products SA	Clinical Study Protocol	Confidential
P1-EXC-01-EU	Version 3.0 / 2 May 2019	Page 15 of 151

The Safety Set consists of all subjects enrolled with signed ICF who have at least one valid safety assessment during the course of the study. The Safety Set will be analyzed by actual exposure (product use exposure).

#### **Endpoint analysis**

A linear mixed effects model will be used to estimate the VO2max values between each arm (*IQOS*-1, SA arm) versus cigarette arm one week after randomization (V4) and after completion of the 12-week training program (V43). The dependent variable will be VO2max with baseline VO2max, arm, sex, age and cigarette consumption as covariates. Appropriate contrasts will be constructed to report an estimate of the difference in VO2max and its 95% confidence intervals within and between each arm. The same analysis will be performed for SA vs *IQOS*-1 arm. Other covariates may be added as deemed appropriate.

To estimate the VO2max values between *IQOS*-1 and *IQOS*-2 arms, the same linear mixed effects model will be used to model the VO2max at V43. The same analysis will be repeated for weight-adjusted and fat-free weight adjusted VO2max.

A linear mixed model will be used to estimate the difference in exercise capacity between each arm (*IQOS*-1, SA arm) versus cigarette arm one week after randomization (V4) and after completion of the 12-week training program (V43). The dependent variable will be the time to complete the test in seconds with baseline exercise capacity (in seconds), arm, sex, age and cigarette consumption as fixed effects. Appropriate contrasts will be constructed to report an estimate of the difference in change in exercise capacity time at V3 and V43 and its 95% confidence intervals as an estimate of the acute effect and training effect, respectively. Other covariates may be added as deemed appropriate. The same analysis will be performed for SA vs *IQOS*-1 arm as well. To estimate the change in exercise capacity between *IQOS*-1 and *IQOS*-2 arm the same linear model will be used to model the change between arms at V43.

An appropriate statistical model will be used to estimate the intensity of exercise training in the various arms over time. Further details will be provided in the SAP.

Estimates of variability from the statistical model (VO2max, exercise capacity, intensity of exercise training) will be reported and may be used to power future similar studies.

Descriptive statistics will be used to present various measures assessing the VO2max, exercise capacity, intensity of exercise training in each arm.

An appropriate statistical model will be used to estimate the changes in physiological parameters and perception of exertion and capacity whilst adjusting for covariates such as age, sex, cigarette consumption or any other clinically relevant covariates of interest. The difference between arms will be estimated and reported together with its 95% confidence intervals. Other covariates may be added as needed.

Data and information contained in this document are considered to constitute trade secrets and confidential commercial information, and the legal protections provided to such trade secrets and confidential information are hereby claimed under the provisions of applicable law. No part of this document may be publicly disclosed without the written consent of Philip Morris Products S.A

Philip Morris Products SA	Clinical Study Protocol	Confidential
P1-EXC-01-EU	Version 3.0 / 2 May 2019	Page 16 of 151

Descriptive statistics of the various measures of physical activity as measured by the mHealth wearable device will be reported. An appropriate statistical (linear or non-linear) model will be used to estimate the levels of activity taking into account clinically relevant covariates and repeated measures over time. Comparisons of physical activity levels for *IQOS*-1 and *IQOS*-2 arm will be reported based on the chosen statistical model.

For each of the biological markers descriptive statistics will be employed to assess the difference between arms. An appropriate statistical model may be employed to estimate differences across arms at V43.

For weight, body fat and waist circumference, descriptive statistics will be employed to assess the changes for each arm. An appropriate statistical model may be employed to estimate differences across arms at V43.

To monitor levels of exposure to CO descriptive statistics of exhaled CO will be summarized and presented for each arm. Descriptive statistics of COHb% in blood, NEQ, NNAL and CEMA in urine will be summarized and presented for each arm. An appropriate statistical model may be employed to estimate differences across arms during the visits where these are measured.

## ABBREVIATIONS AND DEFINITIONS OF TERMS

## **Abbreviations**

AE	Adverse event
AEECS	As Exposed Exercise Compliant Set
BMI	Body mass index
BoExp	Biomarker of exposure
Bpm	Beat per minute
CEMA	2-cyanoethylmercapturic acid
CI	Confidence interval
СО	Carbon monoxide
СОНЬ	Carboxyhemoglobin
CRF	Case report form
CRO	Contract research organization
CSR	Clinical study report
CTCAE	Common terminology criteria for adverse events and common toxicity criteria
CTMS	Clinical trial management system
CV (documentation)	Curriculum vitae
CV (statistics)	Coefficient of variation
DMP	Data management plan
ECG	Electrocardiogram
EOS	End of study
FAS	Full analysis set
$FEV_1$	Forced expiratory volume in 1 second
FTND	Fagerström test for nicotine dependence (revised version)
FVC	Forced vital capacity
GCP	Good Clinical Practice
GH	Growth hormone
Hb	Hemoglobin

#### **Confidentiality Statement**

Philip Morris Products SA	Clinical Study Protocol	Confidential
P1-EXC-01-EU	Version 3.0 / 2 May 2019	Page 24 of 151

HbA1c	Hemoglobin A1c
HDL	High-density lipoprotein
HIV	Human immunodeficiency virus
HPHCs	Harmful and potentially harmful constituents
HR	Heart rate
hs-CRP	High sensitivity C-reactive protein
ICF	Informed consent form
ICH	International Conference on Harmonization
IEC	Independent Ethics Committee
IP	Investigational product
IPAQ	International Physical Activity Questionnaire
LDL	Low-density lipoprotein
LLN	Lower limit of the normal range
LLOQ	Lower limit of quantification
MedDRA	Medical dictionary for regulatory activities
NEQ	Nicotine equivalents
NNAL	Total 4-(methylnitrosamino)-1-(3-pyridyl)-1-butanol
NRT	Nicotine replacement therapy
PMI	Philip Morris International
QC	Quality control
RPC	Rating of Perceived Capacity
RPE	Rate of Perceived Exertion
SA	Smoking abstinence
SAE	Serious adverse event
SAP	Statistical analysis plan
SOP	Standard operating procedure
SPI	Summary of Product Information

